5.1.1.2.4 Definition of Baseline values

Unless otherwise specified, the Baseline value for the Treatment Period is defined as the most recent (date/time considered) non-missing value obtained prior to the administration of the first study dose. If there are multiple assessments on that day then the time will be considered for the selection of the appropriate measurement. For parameters with no Baseline value as per schedule of assessments the screening value will be set as Baseline value. If a Baseline measurement is not available but an unscheduled measurement occurs after the planned Baseline measurement time point but before dosing, then the unscheduled measurement will be used.

For participants who received placebo in the Treatment Period, the value obtained prior to the first administration of Zilucoplan will occur on the Day E1 (Day 57) visit during the Extension Portion of the study and this will be the Baseline value for them for any summary tables during the Extension Portion of the study. If Day 57 dose is missing the last non-missing dose on placebo during the Main Portion will define the baseline date for the placebo patients who change to active in Extension Portion.

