5.6.4.4.2 Immunogenicity

Blood samples for ADA assessment will be collected prior to dose administration at baseline (screening data will be considered as baseline data for ADA assessments), Day 8, Day 29 and Day 57 as well as Day E8, Day E28, Day E57, Day E117 and every 3 months after, including

final Extension visit in all participants prior to drug administration. These samples will be used to investigate and characterize any ADA response over time in SS.

- Sample values that are either ‘negative screen’ or ‘positive screen’ and ‘negative immunodepletion’ will be defined as **ADA negative**
- Sample values that are ‘positive screen’ and ‘positive immunodepletion’ will be defined as **ADA positive**
- Samples that could not be tested for ADA status due to inadequate sample volume, mishandling, or errors in sample collection, processing, storage, etc, will be defined as **Missing**

Sample neutralizing antibody (NAb) status (positive/negative/missing) will be determined for ADA positive samples.

The following ADA classifications will be derived from the sample ADA status:

Table 5–2: ADA Classification

Classification	Classification Label	Definition
1	Pre-ADA negative – treatment induced ADA negative	Participants who are ADA negative at baseline and ADA negative at all sampling points post-baseline.
2	Pre-ADA negative – treatment induced ADA positive	Participants who are ADA negative at baseline and ADA positive at any sampling point post-baseline. It also includes participants who have a missing pre-treatment sample (either missing or insufficient volume) at baseline with one or more ADA positive post-baseline samples.
3	Pre-ADA positive – treatment reduced ADA	Participants who are ADA positive at baseline, and ADA negative at all sampling points post-baseline (including the Extension Portion of the study).
4	Pre-ADA positive – treatment unaffected ADA	Includes participants who are ADA positive at Baseline and ADA positive at any sampling point post-Baseline (including Extension Portion) with titer values of the same magnitude as baseline (less than a predefined fold difference from the baseline value which will be defined within the validation of the assay, i.e. minimum significant ratio of the assay).

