5	Pre-ADA positive – treatment boosted ADA positive	Includes participants who are ADA positive at Baseline and ADA positive at any sampling point post-Baseline (including Extension Portion) with increased titer values compared to baseline (greater than a predefined fold difference increase from Baseline value which will be defined within the validation of the assay i.e. minimum significant ratio of the assay).

Classification	Classification Label	Definition
6	Inconclusive	Participants who have an ADA positive Baseline sample and some post-Baseline samples are missing, while other post-Baseline samples are ADA negative.
7	Treatment emergent ADA positive	Combination of 2 and 5.
8	Pre-ADA positive	Combination of 3, 4, and 5.

In addition to the ADA classifications above, for the purpose of evaluations of the impact of ADA on plasma concentrations and efficacy and safety endpoints, the following definitions will be used:

- Cumulative ADA status (positive/negative). If a participant had at least one positive sample at any time point up to and including the given time point, that participant will be counted as positive at that time point, regardless of any subsequent negative measurements. Thus, the number of participants included in the summary of positive and negative samples will vary by time point for each IMP.
- Overall ADA status. A participant will be classified as overall ADA Positive if at least one post-baseline measurement is positive. A participant will be classified as overall ADA negative if at all post-Baseline visits the ADA status is Negative.

The ADA of Zilucoplan will be measured using a three-tiered assay approach: screening assay, confirmatory assay and titration assay. Any sample confirmed positive for ADA will be assayed to determine whether there is neutralizing potential.

The following tables will be presented on the SS.

- Number and percentage of participants with positive, negative or missing sample ADA status at the time of each visit and all visits by IMP.
- Number and percentage of participants in each of the ADA classifications presented in [Table 5-2](#) by IMP.
- Number and percentage of participants in each of the NAb classifications presented in [Table 5-2](#) by IMP.

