- The prevalence of immunogenicity (Classification 2, 3, 4 and 5), defined as the (cumulative) proportion of participants having ADA positive samples (including pre-ADA positive) at any point up to and including that time point will be summarized by IMP and total. Missing samples will not be included in the denominator.
- The same table will be repeated for Nab (cumulative and overall Nab status will be defined as described above for ADA).
- The first occurrence of treatment-emergent ADA positive will be summarized using frequency and percentage at each post-baseline visit by IMP group. Participants will be counted only once in the numerator based on the earliest visit at which treatment-emergent

ADA positivity is observed. At other visits, participants will be counted in the denominator (assuming a measurement is available). Missing measurements will not be included in the denominator.

- A summary table of all immune related TEAEs by ADA status will be presented by IMP group. For this summary, participants will be presented for TEAEs occurring prior to becoming treatment emergent ADA positive, TEAEs occurring after becoming TE ADA positive and TEAEs for participants who remained TE ADA negative (classifications 1,3,4).
 - Notes: Study physician/safety physician/safety lead will mark the Preferred Term of immune related AEs based on an excel output of all TEAEs (blinded) after database lock. The marked AEs will be used for the summary.

The results for the ADA assessments will be listed by IMP group and timepoint, including the screening assay, confirmatory assay, ADA titer, NAb titer, PK concentration, change from Baseline, treatment-emergent ADA status and ADA classifications. In addition, time since administration of IMP will be reported (in days).

A TEAE overview table will be presented for active treatment by ADA status. Additionally, the number and percentage of participants who experience some AEs (Hypersensitivity reactions, injection sites reactions as defined in Section 5.6.3 and autoimmune disorders) will be presented by SOC and PT and by ADA Status. Autoimmune disorders will be defined if HLT is in “Autoimmune disorders”. For these summaries, participants will be presented for TEAEs occurring prior to becoming treatment emergent ADA positive, TEAEs occurring after becoming treatment emergent ADA positive, and TEAEs for participants who remained TE ADA negative (classifications 1,3,4,6).

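### The ADA and NAb rules in SAP 5.6.4.4.2 conflict, overlap or leave gaps, so several immunogenicity rates are inconsistent or not uniquely defined

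*SAP*

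**What the plan says.** All of this is in SAP 5.6.4.4.2 (Immunogenicity, with Table 5-2) unless noted.

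- **Prevalence.** "The prevalence of immunogenicity (Classification 2, 3, 4 and 5), defined as the (cumulative) proportion of participants having ADA positive samples"; the sentence goes on to include pre-ADA-positive participants, at any point up to the visit in question. The next sentence adds: "Missing samples will not be included in the denominator".
- **Class 6, Inconclusive.** "Participants who have an ADA positive Baseline sample and some post-Baseline samples are missing, while other post-Baseline samples are ADA negative".
- **Class 8, pre-ADA positive.** "Combination of 3, 4, and 5". Class 7, treatment-emergent (TE) ADA positive, combines classes 2 and 5.
- **TE ADA negative.** The summary of immune-related TEAEs by ADA status uses classes 1, 3 and 4. The summaries of hypersensitivity, injection-site and autoimmune events use "participants who remained TE ADA negative (classifications 1,3,4,6").
- **Classes 1 and 3** require a negative result at every post-baseline sampling point. **Classes 4 and 5** need a positive sample at any post-baseline point: class 4 with a titer within a predefined fold of baseline, class 5 with a titer raised beyond that fold.
- **NAb.** "Sample neutralizing antibody (NAb) status (positive/negative/missing) will be determined for ADA positive samples". The Table 5-2 classes and the prevalence table are then to be produced for NAb as well.
- **Baseline.** For ADA, "screening data will be considered as baseline data for ADA assessments". For participants who received placebo in the Main Portion, SAP 5.1.1.2.4 says that "the value obtained prior to the first administration of Zilucoplan will occur on the Day E1 (Day 57) visit", and makes this their Baseline for Extension summary tables.

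**The concern.** Presence of anti-drug antibodies is a listed safety endpoint (SAP Table 1-1, Other Safety Endpoints), and adverse events are tabulated by these classes. The classes therefore have to place each participant once, and every list built on them has to agree with its own definition.

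They do not. A programmer who follows the class lists undercounts pre-ADA-positive participants. Class 6 participants and their events appear in no ADA-status column of one adverse-event table and in the negative column of the others. A participant in both class 4 and class 5 is TE ADA negative and TE ADA positive at once. Where a pattern fits no class, or a NAb denominator is not stated, someone must invent the rule during programming, possibly after unblinding.

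**Working it through.** The plan states no immunogenicity rate or target, so there is no figure to reproduce. The check applies the Table 5-2 definitions to every possible Main Portion pattern and then works simple proportions.

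**Inputs.** Post-baseline ADA samples at Days 8, 29 and 57 (SAP Table 1-2); 12 participants per arm (SAP 1.2); class definitions as above. Each sample is negative, positive or missing. For baseline positives, a positive sample has a titer that is reduced beyond the fold, the same, or raised beyond the fold.

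**1. Baseline positive: 5^3 = 125 patterns.**
- Class 3 only: 1. Class 4 only: 37. Class 5 only: 37. Classes 4 and 5 together: 24. Sum: 1 + 37 + 37 + 24 = 99, all counted in prevalence.
- Outside classes 2 to 5: 125 - 99 = 26. Of these, 6 are class 6 (a mix of negative and missing: 2^3 - 2 = 6).
- The other 20 fit no class: 19 have at least one reduced-titer positive and none at the same or a raised titer (3^3 - 2^3 = 19), and 1 has every post-baseline sample missing.

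**2. Baseline negative, never positive: 2^3 = 8 patterns.** Only the complete all-negative pattern is class 1. The other 7 fit no class, because class 6 admits only baseline positives.

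**3. Baseline missing, never positive: 8 patterns.** None fits a class.

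These are counts of patterns, not probabilities.

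**4. How often a sample is missed.** The documents give no rate. Assume 2%, 5% or 10% missing per sample, independently. Then 1 - 0.98^3 = 5.9%, 1 - 0.95^3 = 14.3% and 1 - 0.90^3 = 27.1% of participants miss at least one of the three Main Portion samples. For those followed through E117 (seven samples) the figures are 1 - 0.98^7 = 13.2%, 1 - 0.95^7 = 30.2% and 1 - 0.90^7 = 52.2%.

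**5. Size for prevalence (assumed counts, one arm of 12).** One participant is 1/12 = 8.3 points. Suppose 3 were ever positive and 1 of them is class 6. By the words of the definition, prevalence is 3/12 = 25.0%. By the class list it is 2/12 = 16.7%, or 2/11 = 18.2% if class 6 also leaves the denominator.

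**6. Size for NAb (assumed counts).** With 3 ADA positive and 1 of them NAb positive, the rate is 1/12 = 8.3% if ADA-negative participants count as NAb negative, and 1/3 = 33.3% if only NAb-tested participants count.

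**7. Baseline for switchers.** SAP Table 1-2 has no Day 1 ADA sample, so Screening is the natural ADA baseline for the Main Portion. Classes 3 to 5 are stated to cover the Extension Portion, and SAP Section 4 puts switchers in both treatment groups according to period. From Screening, one classification would span placebo and zilucoplan samples. From Day E1 it would not, and Table 1-3 schedules an ADA sample at that visit. Section 5.6.4.4.2 does not say which rule applies.

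**The case against.** **Stronger readings that the text does not support**
- A reader might infer that baseline-positive participants as a group fall out of prevalence. They do not: the sentence includes them in words, and classes 3, 4 and 5 are all baseline positive. The gap is class 6 and the unclassified patterns.
- A reader might infer two meanings of an ADA-negative sample. There is one sample-level definition; the conflict concerns the participant-level TE-negative group.
- A reader might infer that cumulative prevalence must fall when a positive participant misses a visit. That is only one reading of the denominator sentence. The cumulative-status rule keeps a participant positive once positive.
- A reader might infer that switchers are firmly tied to Screening. Section 5.1.1.2.4 points to Day E1, so this is an unreconciled conflict.

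**Points in the plan's defence**
- The requirement for negative results at all points could be taken to mean all available points. But class 3 uses the same wording, and on that reading a baseline positive with one negative and one missed sample would be in classes 3 and 6 together. A separate class 6 makes sense only on the literal reading.
- The SAP reserves the missing label for samples that could not be tested, so an ADA-negative sample not sent for NAb testing is not clearly missing. That argues against the 33.3% figure. But SAP 5.1 bases safety percentages on participants with observed data, which points the other way. The status remains unstated.
- Per-visit ADA counts and full listings are planned, so the rates could be recomputed. That stands, and it limits the harm.

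**Conclusion.** The point holds as a set of conflicts and gaps in wording. Three are errors as written: class 6 is left out of class 8 and of the prevalence list, the TE-negative group has two definitions, and classes 4 and 5 overlap. Three leave the result open: patterns without a class, NAb status of ADA-negative samples, and the ADA baseline for switchers.

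With a full denominator of 12, each participant affected moves a rate by up to 8.3 points. The NAb denominator can matter more: 33.3 - 8.3 = 25.0 points in the assumed example. If nobody is class 6 or unclassified, the two prevalence readings agree. How many participants are affected depends on missed samples and baseline positivity, which the documents do not quantify, although SAP 5.1.1.8.2 expects missing data from COVID-19.

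The tables are descriptive. No hypothesis test, alpha allocation or sample size depends on them.

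**What to change.** Amend Table 5-2 and the list of tables that follows it:

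- Set class 8 to 3 + 4 + 5 + 6. Define prevalence as any positive sample to date, with class list 2 + 3 + 4 + 5 + 6.
- Use one TE ADA negative list, 1, 3, 4, 6, in both sets of adverse-event tables. The documents do not dictate that class 6 belongs there; what matters is a single list.
- Give class 5 precedence over class 4, and assign baseline positives with only same or reduced titers to class 4. Placing reduced titers in class 3 instead would leave class 8, prevalence and the TE-negative group unchanged, since both classes are in all three.
- Define class 1 on available samples, with at least one post-baseline result.
- Widen Inconclusive to never-positive participants with a missing baseline and to participants with no post-baseline result. List those who are not baseline positive separately, so that they do not enter class 8 or the prevalence count.
- Count ADA-negative samples as NAb negative.
- State that for placebo switchers the zilucoplan-period classification uses the Day E1 pre-dose sample as baseline, in line with 5.1.1.2.4.

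Applied to the same Main Portion patterns, these rules place each one exactly once. Baseline positive: 61 class 5 + 56 class 4 + 1 class 3 + 7 class 6 = 125. Baseline negative: 19 class 2 + 7 class 1 + 1 separately listed Inconclusive = 27. Baseline missing: 19 class 2 + 8 separately listed Inconclusive = 27.

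The cost is SAP wording and derivation code. No new samples or visits are needed, because the Day E1 sample is already scheduled.

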- Before the pandemic: a TEAE will be assigned to this period if the start date of the event is on or after the date of the first administration of study drug on Day 1 but before the cut-off date of 11th MAR 2020.
- During/after the pandemic: a TEAE will be assigned to the during/after the pandemic Period if the start date of the event is on or after the date of the first administration of study drug on Day 1 but after the cut-off date of 11th MAR 2020.

A TEAE will be counted as related to study drug if the response to the question “Relationship to Study Medication” is “Related”. Severe TEAEs are those with CTCAE Grade 3 or above, or those without a CTCAE grading classified as ‘severe’ by the Investigator. If a participant reports the same event with different relationship assessments, then participant will be counted under both related and not related categories.

Adverse events will be presented as “number of participants (percentage of participants) [number of events]”. In this style of output, “[number of events]” will include all cases of an AE including repeat occurrences in individual participants, while “number of participants” will count each participant only once.

TEAE Summaries will be reported separately within the Main Portion and within the Main and Extension Portion of the study and presented by primary system organ class (PSOC) and preferred term (PT) within each IMP. PSOCs will be sorted alphabetically. PTs will be sorted by decreasing frequency of Zilucoplan within each PSOC; ties will be sorted alphabetically within Zilucoplan. TEAEs will be mapped to a study portion based on the onset date.

The following summaries will be produced:

- TEAE overview table in SS and SS_{NOCOVID-19}, displaying participants with at least one TEAE, with at least one TEAE before/after 11th March 2020, with at least one serious TEAE, with at least one TEAE resulting to permanent withdrawal from study medication, with at least one drug-related TEAE and with at least one TEAE leading to death
- TEAEs by PSOC and PT, in SS
- TEAEs by PSOC and PT by COVID-19 period, in SS
- Serious TEAEs by PSOC and PT in SS
- Serious TEAEs by PSOC and PT for each COVID-19 period, in SS
- TEAEs by PSOC, PT and maximum CTCAE V5.0 Grade, in SS
- TEAEs by PSOC, PT and maximum relationship, in SS
- Serious TEAEs by PSOC, PT and maximum relationship, in SS
- Fatal TEAEs by PSOC, PT and maximum relationship, in SS

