- Non-Serious TEAEs by PSOC and PT of at least 5% within any IMP (Main Portion) or active treatment (Extension Portion), in SS
- TEAEs by PSOC and PT leading to drug discontinuation, in SS
- TEAEs by PSOC and PT leading to death, in SS

Of note, the following are not considered to be AEs despite requiring hospitalization:

- Pre-existing conditions that, in the opinion of the investigator, did not worsen or progress during study participation
- Routinely scheduled procedures or treatments
- Elective procedures that were scheduled prior to study participation (i.e., signing of the ICF)

Safety tables for the combined Main and Extension Portion of the study, will display the Treatment Emergent Adverse Event Incidence Rate (AEIR) per 100 patient-years of Zilucoplan treatment (thus no placebo arm to be summarized due to limited exposure time as compared to active). Tables will include the PEY per 100 patient years (as defined in Section 5.6.1), number and percentage of participants with a particular TEAE, the exposure adjusted incidence rate (EAIR) followed by 95%CI and the exposure adjusted event rate (EAER):

- EAIR for TEAEs by PSOC and PT, in SS
- EAIR for serious TEAEs by PSOC and PT, in SS

The EAIR is defined as the number of study participants with a specific new TEAE divided by the duration of exposure of all participants (scaled to 100 participant years). The time at risk for a study participant is censored at the date of this event. If a study participant has no events, the total time at risk (i.e. exposure) is used.

Exact Poisson 95% CIs for EAIR are calculated using the relationship between the Poisson and the Chi-square distribution (Ulm, 1990; Fay and Feuer, 1997):

$$\text{Lower Confidence Limit} = x_{2n,\alpha/2}^2/2$$

$$\text{Upper Confidence Limit} = x_{2n(n+1),1-\alpha/2}^2/2$$

where n stands for the number of participants with a specific TEAE for the incidence rate of interest and is the basis for the number of the degrees of freedom for the chi-square quantile for the upper tail probability χ^2 .

The EAER is defined as the total number of TEAEs including repeat occurrences in individual study participants divided by the total time at risk scaled to 100 patient-years. No confidence interval will be computed for the EAER.

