Should an Adverse Event of Interest has not occurred during the study, the corresponding line should be included with zero occurrences.

The following tables will be created:

- TEAEs of interest by PT, in SS,
- EAIR for TEAEs of interest by PT, in SS (combined Main and Extension Portion among participant received at least one dose Zilucoplan).

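### Adverse events by ADA status are shown as counts and percentages without time at risk, so the before, after and remained-negative columns cannot be compared

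*SAP*

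**What the plan says.** SAP 5.6.4.4.2 plans three sets of adverse-event summaries by ADA status: immune-related TEAEs, a TEAE overview for active treatment, and a table of hypersensitivity reactions, injection-site reactions and autoimmune disorders. In each, events are divided by when they occurred. For the immune-related table the wording is "participants will be presented for TEAEs occurring prior to becoming treatment emergent ADA positive, TEAEs occurring after becoming TE ADA positive", plus a column for participants who remained treatment-emergent ADA negative. The other two use the same three-way split.

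The measure is explicit only for the hypersensitivity, injection-site and autoimmune table: "the number and percentage of participants who experience some AEs". The other two name no measure, so the general display of SAP 5.6.2 applies: "number of participants (percentage of participants) [number of events" in brackets. SAP 5.1 has a general rule for percentage denominators, but it does not say how that rule works for a column that is a period of time rather than a group of people.

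ADA samples are taken at Days 8, 29 and 57, again at E8 and E28 (E29 in the schedule table), then at "Day E57, Day E117 and every 3 months after". TEAEs count until 40 days after the last dose, or the last visit if earlier (SAP 5.6.2). The Extension lasts 18 months in France and is open-ended elsewhere (Protocol 7.2).

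Elsewhere the SAP does adjust for exposure. Section 5.6.2 plans "EAIR for TEAEs by PSOC and PT, in SS", and Section 5.6.3 plans "EAIR for TEAEs of interest by PT, in SS", both for the combined Main and Extension data. Section 5.6.2 also leaves placebo out of the combined tables: "no placebo arm to be summarized due to limited exposure time as compared to active". No exposure-adjusted rate is planned by ADA status.

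**The concern.** The purpose of these tables is to show whether ADA affects safety. A percentage with at least one event rises with the length of time observed, and so does a raw event count. Each converter's follow-up is cut in two at first positivity, and the two parts are equal only by coincidence. A participant who never converts contributes all follow-up to one column. A difference between columns can therefore come from observation time alone: it can suggest an ADA-related reaction that does not exist, or hide one that does. Hypersensitivity and injection-site reactions get an exposure-adjusted rate overall, but not in the split by ADA status, where exposure may be most uneven.

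**Working it through.** The documents give no figure to reproduce: they state neither event rates, nor conversion dates, nor period lengths by ADA status. The check asks what the planned display would show if ADA had no effect.

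**Inputs from the documents.** Possible dates of first positivity are the ADA sampling visits. Day E1 is Day 57, so day En is study day 56 + n (E57 is Day 113, E117 is Day 173). Eighteen months is about 548 days (18 × 365.25/12). Counting from Day 57 this ends on Day 604, and 40 more days give Day 644. For a participant who does not enter the Extension, 40 days counted from Day 57 end on Day 96.

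**Assumptions.** The event rate is constant, the same before and after, and unrelated to ADA. It is set at 0.5 first events per participant-year and varied from 0.2 to 2. All converters in a row convert at the same visit, they are the denominator of both columns, and an event before does not remove them from the after column.

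**Formulas.** For first positivity on day v and follow-up to day e:
- before = v − 1 days; after = e − v + 1 days
- expected percentage = 1 − exp(−rate × days / 365.25)

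**Example.** v = 29, e = 644. Before: 28 days, 1 − exp(−0.5 × 28/365.25) = 3.8%. After: 616 days, 1 − exp(−0.5 × 616/365.25) = 57.0%.

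| First positive | Follow-up to | Days before / after | Length ratio | % before / after |
|---|---|---|---|---|
| Day 8 | Day 644 | 7 / 637 | 91 | 1.0 / 58.2 |
| Day 29 | Day 644 | 28 / 616 | 22 | 3.8 / 57.0 |
| Day 57 | Day 644 | 56 / 588 | 10.5 | 7.4 / 55.3 |
| E57 | Day 644 | 112 / 532 | 4.75 | 14.2 / 51.7 |
| E117 + 3 months | Day 644 | 263 / 381 | 1.45 | 30.2 / 40.6 |
| E117 + 6 months | Day 644 | 354 / 290 | 0.82 | 38.4 / 32.8 |
| E117 + 12 months | Day 644 | 536 / 108 | 0.20 | 52.0 / 13.7 |
| Day 8 | Day 96 | 7 / 89 | 12.7 | 1.0 / 11.5 |
| Day 29 | Day 96 | 28 / 68 | 2.4 | 3.8 / 8.9 |
| Day 57 | Day 96 | 56 / 40 | 0.71 | 7.4 / 5.3 |
| Day 29 | Day 57 | 28 / 29 | 1.04 | 3.8 / 3.9 |

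**Remained-negative column.** With the same rate and follow-up to Day 644, it would show 1 − exp(−0.5 × 644/365.25) = 58.6%. With follow-up to Day 96 it would show 1 − exp(−0.5 × 96/365.25) = 12.3%. Both exceed either converter column with the same follow-up.

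**Other rates.** The direction does not change. Day 29 with follow-up to Day 644 gives 1.5% against 28.6% at 0.2 per participant-year, 7.4% against 81.5% at 1, and 14.2% against 96.6% at 2. Day 57 with follow-up to Day 96 gives 3.0% against 2.2%, 14.2% against 10.4%, and 26.4% against 19.7%.

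**With the SAP's own rate.** SAP 5.6.2 defines it thus: "The EAIR is defined as the number of study participants with a specific new TEAE divided by the duration of exposure of all participants", with time censored at the event. For N participants observed for t years, expected first events are N(1 − exp(−rate × t)) and expected time at risk is N(1 − exp(−rate × t))/rate. The quotient is the rate itself: 50 per 100 participant-years in every column and every row above, a ratio of 1.0.

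**The case against.** A reader might infer that the after percentage is higher by construction because the periods differ many-fold. The documents do not support that. They give no conversion dates or period lengths, the two periods can be nearly equal (Day 29 with data to Day 57), and the direction reverses when first positivity falls in the second half of observed time. That reversal occurs even with an 18-month Extension.

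Other points against giving this much weight:

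- **Main Portion tables.** TEAE summaries are also reported for the Main Portion alone, so the largest contrasts belong only to the combined tables. This stands, although an imbalance in either direction remains in the Main data.
- **Zilucoplan starters only.** Placebo participants first receive zilucoplan at E1, so the Day 8 and Day 29 rows do not describe them. This also stands, but E8 and E29 lie as far from E1 as Days 8 and 29 lie from Day 1, so the same issue arises if exposure is counted from first zilucoplan.
- **Listings.** With about 24 participants, the planned ADA and adverse-event listings allow timing to be checked case by case. This lowers the priority but does not make the table readable on its own.
- **Table specifications.** These are in a separate document not available here and may define denominators. That would not by itself supply time at risk.
- **Weakness of the rate.** It is easy to interpret only if the event rate is roughly constant. If reactions cluster soon after the first doses, a short before period is inflated: one event in 7 days at risk is 100 × 365.25/7, about 5,200 per 100 participant-years. The split date is also only as exact as the sampling interval, which reaches 3 months. This is a good reason to show counts and rates together and not to replace one with the other.

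**Conclusion.** The concern holds in this form: the three columns are not comparable because exposure differs and is not shown. With no ADA effect, the percentage is higher in whichever of a converter's two periods is longer. That is the after period when positivity comes in the first half of observed time, and the before period otherwise. The no-effect contrast can be large (3.8% against 57.0%), negligible (3.8% against 3.9%) or reversed (7.4% against 5.3%). These sizes rest on an assumed constant rate and on illustrative conversion dates. The number of ADA-positive participants is unknown and probably small. The tables are descriptive, and no endpoint test or hypothesis depends on them. It is a worthwhile, inexpensive improvement to the safety reporting.

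**What to change.** In SAP 5.6.4.4.2, keep the planned counts and percentages, and for each of the three columns add:

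1. the number of participants with any exposure in that period, used as the denominator of the percentage;
2. total person-time, with each converter's exposure split at the date of the first treatment-emergent positive sample;
3. the exposure-adjusted incidence rate and event rate of SAP 5.6.2.

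State whether a participant with an event before conversion is again at risk for that event afterwards. Add a footnote that the rates assume a roughly constant hazard and that the conversion date is known only to within the sampling interval.

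The cost is SAP wording and some programming, with no new data. With few ADA-positive participants the rates will be imprecise, and a short before period can give an extreme value, so they should be read beside the counts.
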